- 3. Do the improvements in functional mobility, quality of life, pain management, and inflammatory biomarkers in knee OA patients differ between those enrolled in the GLA:D[™] and the JointEffort education and exercise programs?
- 4. How does the cost of the programs compare to health outcomes and how much are participants willing to pay to participate in the GLA:D and JointEffort programs?

OBJECTIVES: The objectives of the proposed study are to 1) assess the association between participation in the GLA: D^{TM} standardized program and functional mobility, quality of life, pain management, and inflammatory biomarkers in knee OA patients, 2) assess the association between participation in the JointEffort individualized program and functional mobility, quality of life, pain management, and inflammatory biomarkers in knee OA patients 3) assess if there are any differences in outcomes between the standardized (GLA: D^{TM}) and individualized (JointEffort) exercise programs, and 4) Assess how the cost of the programs compare to health outcomes and how much patients are willing to pay to participate in the GLA:D and JointEffort programs.

METHODOLOGY:

Study Participants: A convenience sample of 100 participants \geq 50 years of age with a primary care physician or orthopedic surgeon knee OA diagnosis will be included in the study. Specifically, 50 individuals will participate in 1) the GLA:DTM program and 50 sex- and age-matched individuals will participate in 2) the JointEffort program. 100 participants is a conservative estimate based on the ability to detect a moderate effect between study groups (1- β =0.8, α =0.05).

Exercise Programs: The GLA:DTM program consists of 1) pre and post program outcome measurement (self-reported and functional outcomes); 2) 2 1-1.5 hour education sessions including information on OA disease characteristics, treatments and self-help strategies; and 3) a neuromuscular exercise (warm-up,

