circuit training, and cool down) training program administered in 1 hour, small (up to 10 persons) groupbased, supervised sessions twice weekly for 6 weeks. The goal of the exercises is to restore neutral, functional alignment of the legs by building compensatory functional stability and improving sensorimotor control. The JointEffort program consists of: 1) one appointment aimed at individualized program design; 2) a nutritional seminar taught by a registered dietician explaining dietary recommendations for OA patients and inflammatory conditions, including weight loss and/or management; and 3) an individualized exercise (strength and neuromuscular training, balance training, and range of motion exercises) training program administered in 1 hour, small (up to 10 persons) group-based, supervised sessions twice weekly for 6 weeks.

Study Outcomes:

1) Participant Characteristics, Adherence, and Medication Use: Demographic (age, sex, height, weight, and body mass index), comorbidity, attendance, exercise log, and medication use details will be recorded at each visit. Adherence will be measured by exercise program attendance (number of sessions).

2) Self-Reported of Symptoms, Function, Quality of Life, and Cost Questionnaire: The following self-report questionnaires will be completed at baseline, 2, and 12 months: the Knee Injury and Osteoarthritis Outcome Score (KOOS) [8], the Intermittent and Constant Osteoarthritis Pain (ICOAP) Score [9], and the EuroQOL-5 Dimensions (EQ-5D-5L) Score [10]. A cost questionnaire will be used to capture information about your employment status, gross income, insurance coverage, willingness to pay, and health care visit.

3) Disease Knowledge and Arthritis-Related Self-Efficacy: The patient knowledge questionnaire on OA (PKQ-OA) [11] and the arthritis self-efficacy questionnaire [12] will be completed at baseline, 2, and 12 months.

4) Physical Function: All participants will complete the 40m Face-Paced Walk Test and the 30s Chair Stand Test [13] at baseline, 2, and 12 months.

5) Biomarker Analysis: A blood serum sample, collected at baseline, 2, and 12 months will be analyzed to assess for inflammatory biomarkers using a Discovery Assay (42 Custom-Plex human assay) with Luminex[®]xMAP technology (Eve Technologies).

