STATISTICAL ANALYSIS: Descriptive statistics (mean (95% CI), proportion (95% CI) or median (range) will be used report the baseline, 2, and 12 month change in self-report, functional and biomarker outcomes, as appropriate. To account for the matched design, mean within-pair difference (95% CI) will be used to compare treatment groups across outcomes. Finally, conditional logistic regression will be used to assess the relationship between attendance (number of sessions) and 12 month change in each outcome.

SIGNIFICANCE: This project will contribute to the understanding of exercise programming prescription for knee OA patients. If GLA:DTM and/or JointEffort support improvements in functional mobility, quality of life, pain management, and inflammatory biomarkers, it could play a role in the implementation strategy for OA patients within the province. Exercise programming has the potential to be implemented in several sites across Alberta, and thus potentially modifying disease progression and possibly delaying total joint replacement.

PROJECT FLOWCHART:

Baseline Appointment Weeks 1-7 Exercise Program (GLA:D™ Canada or JointEffort)		2 Months Assessment & Questionnaires
TIME POINT	GLA:D™ Canada Group	JointEffort Group
	(Standardized Exercise Program)	(Individualized Exercise Program)
Baseline	 The GLA:D[™] Canada program will be 	1) The JointEffort program will be
Appointment	explained.	explained.
	2) Participants will be asked to complete	2) Participants will be asked to complete
	the questionnaires (KOOS, EQ-5D-5L,	the questionnaires (KOOS, EQ-5D-5L,
	ICOAP, PKQ-OA, the arthritis self-efficacy	ICOAP, PKQ-OA, the arthritis self-efficacy
	questionnaire and the Arthritis Cost	questionnaire and the Arthritis Cost
	Questionnaire Baseline).	Questionnaire Baseline).
	3) Demographics, symptoms,	3) Demographics, symptoms, comorbidities,
	comorbidities, and medication use will be	and medication use will be recorded.
	recorded. 4) Blood draw for biomarker analysis.	4) Blood draw for biomarker analysis.5) Participants will be asked to complete
	5) Participants will be asked to complete	physical function tests (40m Face-Paced
	physical function tests (40m Face-Paced	Walk Test and the 30s Chair Stand Test).
	Walk Test and the 30s Chair Stand Test).	6) Individualized program design.
Weeks 1-7	1) Two education sessions about OA (1-	1) One nutritional seminar taught by a
	1.5 hours each), including the	registered dietician explaining dietary

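### The pair-conditional attendance analysis states no program term, so it can credit a program difference to sessions (or hide a session effect) if the two programs also differ in mean attendance

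*Combined protocol and SAP*

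**What the plan says.** Under Study Participants the plan recruits "A convenience sample of 100 participants"; "50 individuals will participate in 1) the GLA:DTM program", and "50 sex- and age-matched individuals will participate in 2) the JointEffort program". No randomisation is stated.

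Under Statistical Analysis the pair is the unit of the treatment comparison: "To account for the matched design, mean within-pair difference (95% CI) will be used to compare treatment groups across outcomes". The next sentence is the whole of the attendance analysis: "conditional logistic regression will be used to assess the relationship between attendance (number of sessions) and 12 month change in each outcome". It names an exposure and an outcome. It does not name the strata, a program term, any other covariate or a within-program analysis. Study Outcomes, item 1, defines adherence as the count of sessions attended.

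On sessions offered, Exercise Programs describes both programs as "supervised sessions twice weekly for 6 weeks", and the Project Flowchart gives the same twice-weekly, six-week schedule for each. The Budget costs 12 exercise sessions per GLA:D class but 11 per JointEffort class, under both Program Instructors and Equipment and Facilities.

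**The concern.** Conditional logistic regression compares people only within a matched set. The pair is the only matched set this plan creates, and it always straddles the two programs. Two GLA:D participants who attended different numbers of sessions are therefore never compared directly, and nor are two JointEffort participants. The analysis sees only how many more sessions the GLA:D member attended than the JointEffort partner.

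That contrast is tied to program. With no program term, a program that is both better and better attended makes sessions look beneficial even if they do nothing. If the less effective program is the better attended one, a real benefit of sessions can be masked. The analysis is planned for every outcome and is the plan's only look at exercise dose.

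**Working it through.** **1. The model.** The plan gives no figure of its own to reproduce here, so start from the likelihood. Let D be GLA:D sessions minus JointEffort sessions within a pair, and suppose 12-month change has been made binary (improved or not). Only pairs in which exactly one member improved contribute:

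logit P(the GLA:D member is the improver) = γ + βD

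Here γ is the program log odds ratio and β the log odds ratio per session. Leaving out program sets γ = 0. If γ is not zero and the mean of D is not zero, β absorbs part of γ. If either is zero, there is no systematic bias.

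**2. Limiting case from the budget.** Program description: 2 × 6 = 12 sessions in each program. Budget: 12 and 11. If 12 and 11 were delivered and everyone attended all of them, D = 12 − 11 = 1 in every pair, and the estimated β would equal γ exactly. For assumed responder rates of 60% and 40%, independent within pairs, that odds ratio is (0.6 × 0.6)/(0.4 × 0.4) = 2.25 per session, all of it due to program.

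**3. The mechanism in closed form.** In the linear pair-difference analogue, with program effect δ, mean attendance gap m and attendance SD s per person, the false slope without a program term is

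δm / (m² + 2s²)

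With assumed δ = 5 points and s = 2.5 (2s² = 12.5):
- m = 0: 0
- m = 1: 5/13.5 = 0.37 points per session
- m = 2: 10/16.5 = 0.61
- m = 3: 15/21.5 = 0.70

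The sign follows δm, so the error can run either way. The plan does not name this linear model; it only shows how the bias arises.

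**4. The planned model, simulated with β = 0.** The documents give no responder rates, program effect or attendance SD, so all of these are assumptions.

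(a) 50 pairs, responders 60% v 40%, attendance SD 2.5, no program term:
- m = 1: median odds ratio per session about 1.06, false positives about 5%
- m = 2: about 1.11, about 12%
- m = 3: false positives about 19%

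(b) Same responder rates, 12 v 11 sessions offered, 85% to 92% attended: odds ratio about 1.2 to 1.4, false positives about 9% to 16%.

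(c) Sensitivity to the program odds ratio (3,000 trials of 50 pairs, about 23 informative pairs each). Odds ratios are exponentials of the median log odds ratio:

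| Sessions offered, % attended | Program OR 2 | Program OR 3 |
|---|---|---|
| 12 v 11, 85% both | e^0.16 = 1.17; 6% false positives | e^0.26 = 1.30; 12% |
| 12 v 11, 92% both | e^0.25 = 1.28; 9% | e^0.41 = 1.51; 21% |
| 12 v 11, 99% both | e^0.59 = 1.80; 25% | e^0.97 = 2.64; 56% |
| 12 v 12, 85% v 75% | e^0.17 = 1.19; 8% | e^0.25 = 1.28; 17% |
| 12 v 12, 85% both | 1.00; 2% | 1.00; 2 to 3% |

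The reference for these rates is not quite 5%. With so few informative pairs the test is conservative, at 2% to 3% when the programs are equally effective.

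**5. Adding a program term.** The median log odds ratio returns to between −0.01 and 0.01 in every setting of (c), with false positives of 0.2% to 3%. The lowest rates come at 99% attendance. D is then almost constant, program and sessions are nearly aliased, and the model has little information on sessions.

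**The case against.** The strongest reply is that both premises are read from a single sentence. The plan does not say that the strata are the pairs, and it does not say that program is excluded; an analyst might well add it. This stands as far as wording goes: the documents support saying that no program term is stated, not that one is ruled out. But conditional logistic regression needs matched sets, the plan has only one kind, and the sentence followed as written gives the biased model. The result depends on the missing term, so it should be written down.

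Second, a reader might infer that the analysis will necessarily mistake program for dose. The documents do not support that. Bias needs unequal mean attendance and unequal program effects together. The program description gives both programs the same schedule, and the one documentary sign of a gap is the budget's single session. Nothing in the documents points to a gap of two or three.

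Third, a reader working from the linear analogue might quote false-positive rates of 32% or about 51% (program effect 10 points, SD of change 15, gaps of two and three sessions). Those rates belong to a model the plan does not name and to a program effect of 10/15 = 0.67 SD. In the planned model, with attendance SD 2.5 and a one-session gap, the rate is about 5%. It rises materially when attendance is more uniform, and the documents do not say how variable attendance will be.

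Fourth, attendance-response is not among the four research questions or objectives, and the comparison of programs by within-pair differences is unaffected. Both points stand and limit the weight of this one.

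Last, the sentence must be rewritten anyway, because the model needs a binary outcome and no cut-off for 12-month change is given. That is a separate gap. Supplying a cut-off would leave this problem in place.

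**Conclusion.** The point holds in a conditional form. As written, the attendance analysis uses only cross-program session differences and states no program term. It can therefore attribute a program difference to sessions, or mask a session effect, when mean attendance and program effect both differ. With either equal, there is no systematic bias.

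The likely size in the planned model is modest to moderate: a false odds ratio per session of about 1.06 to 1.4 and false positives of about 5% to 16%. This covers gaps of one to two sessions at attendance SD 2.5, and 12 v 11 sessions offered at 85% to 92% attendance. It rests on assumed responder rates of 60% v 40%, 50 complete pairs and no true session effect. It would be larger with near-complete attendance at unequal session counts.

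It would be wrong to conclude that the main program comparison is compromised, or that a false dose finding is probable. This is a correction to a secondary analysis, worth making because it is cheap.

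**What to change.** Preferred: estimate the attendance-outcome association within each program and combine the two estimates, in one model that uses all participants and includes program, sex and age. Matching is on sex and age only, so those covariates carry it. At minimum, keep the pair-conditional model and add a program term (an intercept in pair-difference form). Name the strata and the covariates in the text. Reconcile the number of sessions between the program description and flowchart on one side and the budget on the other.

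The cost is a sentence or two, one extra parameter and some precision. In the linear analogue (program effect 10, gap of two sessions, SD of change 15), the SD of the slope rises from about 0.80 to 0.88, a factor of 0.88/0.80 = 1.10. The loss is larger in the pair-conditional form when attendance is near complete, because program and sessions are then almost aliased. Using all participants recovers some of it. In the linear case with a program term, and no correlation between partners beyond age and sex, the approximate standard error is 15/(2.5 × √50) = 0.85 from 50 pair differences and 15/(2.5 × √100) = 0.60 from 100 individuals.

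Neither version makes the slope a causal dose effect. Attendance is self-selected, so the result should be reported as an association.

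### The attendance regression names no covariate, so as written it is open to confounding by baseline status that the study already records

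*Combined protocol and SAP*

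**What the plan says.** The whole attendance analysis is one sentence under STATISTICAL ANALYSIS: "conditional logistic regression will be used to assess the relationship between attendance (number of sessions) and 12 month change in each outcome". It gives a method, an exposure and an outcome. Neither that section nor any other names an adjustment variable for it.

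The exposure is defined under Study Outcomes, item 1, as the number of exercise sessions attended. Under METHODOLOGY, Study Participants, the sample is "A convenience sample of 100 participants", and the second group is formed so that "50 sex- and age-matched individuals will participate in 2) the JointEffort program". Sex and age are the only matching factors.

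The candidate covariates are already collected. Study Outcomes, item 1: "Demographic (age, sex, height, weight, and body mass index), comorbidity, attendance, exercise log, and medication use details will be recorded at each visit". Item 2, on KOOS, ICOAP and EQ-5D-5L: "The following self-report questionnaires will be completed at baseline, 2, and 12 months". Items 4 and 5 place the function tests and the serum sample at the same three time points.

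**The concern.** The number of sessions attended is chosen by the participant; it is not an assigned dose. Pain, function, BMI, comorbidity and medication use can plausibly affect both how often someone attends and how much they change by 12 months. Conditioning on the matched pair removes only what the pair shares by design, which is sex and age.

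Using change from baseline as the outcome does not settle the matter. Change is usually negatively correlated with the baseline score, because people who start worse tend to improve more through regression to the mean. If attendance is related to baseline severity, that link can pass into the attendance-change association. If sicker people attend more, an association is created or inflated. If healthier people attend more, a real one is hidden or reversed. The same sentence governs every outcome, so the exposure to bias recurs in each.

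**Working it through.** **The plan's own figure.** There is none for this analysis. The sample size statement, "100 participants is a conservative estimate based on the ability to detect a moderate effect between study groups", concerns the group comparison, so there is nothing to reproduce here.

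**Inputs from the documents.** 50 matched pairs; conditional logistic regression; attendance as exposure; 12-month change as outcome; no covariate.

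**Inputs assumed.** The documents give no correlations and no cut-point for change.
- r, the correlation of attendance with baseline score: 0.2 to 0.4
- rho, the correlation of baseline with 12-month score: 0.7 to 0.3
- Equal SDs at both times, and a higher score meaning better health
- Improvement defined by a median split of change
- All 50 pairs complete, and no true attendance effect
- Attendance independent of the 12-month score given baseline

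**Step 1: direction and size on the continuous scale.** With unit SDs, cov(attendance, change) = r·rho − r = −r(1 − rho), and SD(change) = √(2(1 − rho)). Hence corr(attendance, change) = −r·√((1 − rho)/2).
- r = 0.2, rho = 0.7: −0.2 × √0.15 = −0.08
- r = 0.3, rho = 0.5: −0.3 × √0.25 = −0.15
- r = 0.4, rho = 0.3: −0.4 × √0.35 = −0.24

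**Step 2: information in the planned model.** Only pairs discordant on the outcome contribute. Under a median split, a pair is discordant with probability 2 × 0.5 × 0.5 = 0.5, so about 25 of 50 pairs are informative.

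**Step 3: the planned model under no true effect (simulation).**

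| r / rho | Odds ratio per SD of attendance, no covariate | False positives, planned model | False positives, unmatched linear test, n = 100 |
|---|---|---|---|
| 0.2 / 0.7 | 0.88 | 4% | 12% |
| 0.3 / 0.5 | 0.78 | 8% | 32% |
| 0.4 / 0.3 | 0.67 | 19% | 68% |

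If sicker people attend more, the odds ratios invert: 1/0.88 = 1.14, 1/0.78 = 1.28, 1/0.67 = 1.49. With the baseline score added, the odds ratio returns to about 1.0. When attendance is unrelated to baseline, the model without covariates gives 0.99 with 3% rejection. The 4% in the first row is therefore essentially no inflation; the other two rows are.

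**Step 4: hiding a true effect.** Assume a true effect of 0.3 SD of change per SD of attendance and a change-baseline correlation of −0.5. The baseline-adjusted odds ratio is about 1.75 to 1.77 in large samples. Without adjustment it falls to 1.27 when attendance correlates +0.3 with baseline, and to 1.08 at +0.5.

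**Step 5: limits of baseline adjustment.** Suppose instead that attendance tracks a stable severity trait of which the baseline score is a noisy measure. Then unadjusted change holds about 5% error, and it is the baseline-adjusted linear test that is biased: about 14% false positives at r/rho of 0.2/0.7, and somewhat over 40% at 0.3/0.5. Neither analysis is safe under every mechanism.

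**The case against.** Much of the case for the plan stands.

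- **Silence is not a commitment.** A reader might infer that the plan commits to an unadjusted model. It does not say so; it is silent. What stands against it is that this document is also the SAP, so silence leaves the choice of covariates until after the data are seen.
- **The large error rates belong elsewhere.** A reader might expect false-positive rates of 12% to 68%. Those apply to an unmatched linear test on 100 people. For the planned model they are too high by a factor of three to four (12/4 = 3, 32/8 = 4, 68/19 = 3.6).
- **Every correlation is assumed.** If attendance is unrelated to baseline, this route of bias is nil, and the direction is unknown in any case. That is fair, and it is why only a range is given.
- **No dose claim is made.** A reader might infer that the study will report a dose-response. The plan speaks of a relationship, and objectives 1 and 2 speak of association. What remains is only a risk of over-reading, since the SIGNIFICANCE section points towards exercise prescription.
- **The analysis is secondary.** No research question or objective concerns attendance. This limits the weight of the point without removing it.
- **A long covariate list would not fit.** About 25 informative pairs support one or two covariates in conditional logistic regression. This objection is correct and shapes the fix.

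**Conclusion.** The concern holds as a gap in specification with a real consequence. Run as written, the attendance analysis is open to confounding by baseline status, BMI, comorbidity and medication use, because matching covers only sex and age and no covariate is named. Under the assumed correlations, the planned model gives a spurious odds ratio per SD of attendance of about 0.88 to 0.67, or 1.14 to 1.49 in the other direction. The false-positive rate runs from no real inflation (4%) to 19%.

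These sizes depend on the assumed correlations, the median split and full follow-up of all pairs; none comes from the documents. The return to 1.0 after adjustment depends on baseline score being the only confounder in the simulation, so adjustment should not be read as a guarantee. The point deserves correction, but it does not touch the main group comparison.

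**What to change.** Under STATISTICAL ANALYSIS:

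1. State that the attendance model for each outcome includes the baseline value of that outcome.
2. Add BMI, comorbidity and baseline medication use only where the model can support them. Conditional logistic regression with about 25 informative pairs allows one or two covariates in all. A linear model of the 12-month score on attendance and baseline score would allow the full set; it should keep age, sex and program as terms, since it no longer conditions on the pair.
3. Report the unadjusted result beside the adjusted one, because baseline adjustment is itself biased if attendance follows a stable severity trait.
4. State that the result is an association, which may partly reflect symptoms influencing attendance, and not an effect of exercise dose.

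The cost is a few sentences of text and some loss of precision from the added terms in a secondary analysis. No new data are needed.
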